4.3 Withdrawal, Discontinuation, and Replacement of Subjects

4.3.1 Withdrawal and Discontinuation

Subjects are free to withdraw consent from participation in the trial at any time and for any reason upon request. Withdrawal from the trial will not affect or prejudice the subjects' further care or treatment.

Subjects may be withdrawn from trial treatment and/or assessments at any time, if deemed necessary by the investigator.

Examples of reasons for withdrawal/discontinuation of subjects from this trial are:

- Screening failure;
- The decision of a subject to withdraw from the trial (i.e. if the subject withdraws informed consent);
- Pregnancy;
- Failure to comply with the trial visits and procedures;
- Subject is lost to follow-up (defined as a subject who has failed to return for two consecutive scheduled visits and cannot be contacted by the study site staff);
- Subject fulfills any other criteria that, in the opinion of the investigator, justifies discontinuation of the subject from the trial.
- Subjects experience side effects and/or require concomitant medications for treatment of HIV infection and/or its complications that are incompatible with continued study treatment (exceptions are permissible but should be discussed with the Sponsor and the medical monitor).

Subjects who withdraw from trial due to withdrawal of consent, inability or unwillingness of the subject to comply with trial procedures or are lost to follow-up are considered as trial dropouts and will not perform the follow-up visits.

Subjects who discontinue treatment with CyPep-1 for safety reasons (Section 7.2.1) or due to concomitant medication or therapy (Section 5.6) will not necessarily be considered withdrawn from the trial unless there are other reasons for withdrawal. They should return for all following visits and assessments until the last follow-up visit. For Arm B, treatment with pembrolizumab may continue at the discretion of the investigator.

A subject may be discontinued from study treatment but continue to be monitored in the study for any of the following reasons:

- Discontinuation of treatment may be considered for subjects who have attained a confirmed complete response (CR) and have been treated for at least 8 cycles (at least 24 weeks), receiving for combination treatment: 2 cycles of the combination including 2 doses of pembrolizumab beyond the date when the initial CR was declared.
- Completion of 18 (for Q6W dosing) administrations (approximately 2 years) with pembrolizumab

(Note: The number of administrations is calculated starting with the first dose of pembrolizumab.)

- Any study intervention-related toxicity specified as a reason for permanent discontinuation as defined in the guidelines for dose modification due to AEs in Section 5.3.6. If CyPep-1 treatment is delayed > 7 days, that dose will be omitted. If the delay of > 7 days is during the TLT observation period, the subject will be replaced.

For Phase I, Phase IIa Arms A and C, if CyPep-1 treatment is delayed for > 6 weeks during the DLT period (first 3 injections), the subject should be discontinued from the trial. For Arm B, treatment with pembrolizumab may continue at the discretion of the investigator. For Arm D, in case CyPep-1 treatment is delayed for > 3 weeks (first 3 injections), the investigator and the Medical Monitor must assess on a case by case basis the decision whether the subject should be discontinued from the trial. Treatment delay due to TEAEs will be considered for treatment discontinuation.

For any subject who is withdrawn or discontinued from the trial, the reason, date and subsequent planned replacement therapy (if applicable), must be recorded in the electronic case report form (eCRF) and in the medical record. (S)AEs ongoing at trial withdrawal will be followed up for outcome information until resolution or stabilization (see Section 7.2.1).

When a subject is withdrawn or discontinued from active trial follow-up after having received at least one intratumoral CyPep-1 injection, and if the subject agreed on the ICF, every effort will be made to report serious adverse events (SAEs) until at least 3 months after the last intra-tumoral CyPep-1 injection administered for both trial phases.

If a subject withdraws consent from specific assessment(s) following intratumoral CyPep-1 injection (i.e. tumor biopsy, radiological or hematological assessments, etc.), all other assessments should be completed as per protocol and a protocol deviation should be recorded for both trial phases.

If a subject is withdrawn or discontinued from the trial, all data collected until the time of withdrawal will be used in the analyses.

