For Phase I and Phase IIa, Arms A, B and C, CyPep-1 will be administered intratumorally Q2W, on Day 1, 15, and 29 of each cycle. In the absence of DLT/TLTs during Cycle 1, treatment continues with Q2W IT injections of CyPep-1. For Arm D, CyPep-1 will be administered intratumorally QW until the second iRECIST/itRECIST assessment at week 16, followed by a Q2W dosing scheme. For all phases/arms, treatment will continue until confirmed PD, unacceptable toxicity, death, or consent withdrawal, loss to follow up, or trial end, whichever occurs first (for discontinuation refer to Section 4.3.1).

Administration will be through a needle inserted trans-dermally. The needle should be redirected along multiple tracks to ensure even dispersion of CyPep-1 throughout the lesion. For Arm C, CyPep-1 will be administered via intralesional injection with ultrasound guidance into one metastatic liver lesion. A detailed guidance for intratumoral administration of CyPep-1 is presented in the Study Procedural Manual.

The CyPep-1 concentration for each dose cohort during dose escalation (Phase I) is as follows:

Dose cohort	CyPep-1 concentration
1	0.5 mg/mL
2	2 mg/mL
3	5 mg/mL

The total amount of CyPep-1 injected will depend on the tumor volume(s). Effort should be made to administer the maximum planned injection volume of CyPep-1 as planned per lesion size.

CyPep-1 Injection Volume:

The volume delivered to each lesion selected for injection will be determined based on the longest diameter measured by the most accurate measurement technique available for each lesion (e.g. caliper, CT, or MRI) at screening and every 8 weeks during the iRECIST/itRECIST assessments. A chosen technique used at screening will be consistently used throughout the study. Lesion sizes need to be checked before each injection by either caliper (mandatory for Arm D and to-be-injected cutaneous/subcutaneous lesions for Phase IIa Arms A and B) or other imaging modalities used to guide CyPep-1 injections, i.e. ultrasound, CT, or MRI. For Arm C, the lesion size measurement will be performed by the same imaging modality used to guide CyPep-1 injections. To ensure consistency of the measurements, the sites need to strive for having the same operator to perform all measurement for a chosen measuring technique. If there are major changes in the lesion size, the injection volume may be adjusted based on the ultrasound measurements per investigator's opinion and consultation with the Medical Monitor is possible.

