24. Continuous Q2W CyPep-1 treatment is planned and until confirmed PD, unacceptable toxicity or consent withdrawal, loss to follow up, or trial end, whichever occurs first. Lesions not originally planned to be injected with CyPep-1 at screening may also be injected per investigator's discretion, if necessary and after consulting with medical monitor. Follow-up visits will follow the interval as defined in **Table 1a/c**. For subjects in the combination arm treatment with pembrolizumab will continue as per SoC following Q6W dosing until PD, unacceptable toxicity or consent withdrawal.

25. Per additional cycles: C2, C3, ...Cn. CXV1 is scheduled 2 weeks after the last CyPep-1 administration (to follow a Q2W administration schedule).

26. If a subject is receiving additional Q2W treatment with CyPep-1, a biopsy of any new injected lesion(s) can be taken (not mandatory) after 6 weeks for each subsequent cycle. A biopsy at CxD1 (pre-dose) is only applicable if any new lesion(s) are selected for CyPep-1 injection (not mandatory). Arrangements to be made for any tumor material to be sent for analysis are described in the laboratory manual. The visit window for biopsies on CxV4 is ± 3 days.

27. Cytokine levels should only be assessed in the first and second cycles of CyPep-1 administration.

28. The visit window for biopsies on C1V4 is ± 3 days.

29. Pembrolizumab administration only in the combination arm (Arm B). Pembrolizumab should be administered as per SOC Q6W independent of other administrations or assessments (see **Section 5.3.2** for details regarding pembrolizumab administration). CyPep-1 should be administered 30 to 60 min after pembrolizumab if on the same day. All safety assessments and safety laboratory testing should be performed on all pembrolizumab administration days as specified in **Table 1c**. Pembrolizumab will be administered using IV infusion after all procedures and assessments have been completed. See **Section 5.3.6.2** for dose modifications and toxicity management. Pembrolizumab will be administered to a maximum of 18 cycles and then stopped.

30. Thyroid panel should include: triiodothyronine (T3) or free triiodothyronine (FT3); free thyroxine (FT4); thyroid stimulating hormone (TSH).

31. The frequency for tumor biopsy is every 6 weeks from D1 if a subject stays on treatment. The biopsy of at least one injected lesion is highly desired but not mandatory.

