3.3 Duration of Subject Participation

Each subject will undergo up to 4 weeks of screening, followed by a DLT/TLT observation period of 6 weeks (5 weeks of CyPep-1 treatment plus 1 week observation). In absence of DLT/TLTs, treatment continues with Q2W intratumoral injections of CyPep-1. For the combination arm (Arm B), plus Q6W administration of pembrolizumab for up to 24 months (18 cycles). For Arm D, after screening, each subject will undergo QW CyPep-1 treatment until the second iRECIST/itRECIST assessment at week 16, followed by a Q2W dosing scheme. Continuous treatment cycles of CyPep-1 and/or pembrolizumab are planned and should follow the Q2W administration schedule until confirmed PD, unacceptable toxicity, death, or consent withdrawal, loss to follow up, or trial end, whichever occurs first.

Hereafter, there will be efficacy (PFS) follow-up every 8 weeks, or until confirmed PD, death, withdrawal of consent, loss of subject to follow-up, or trial end, whichever occurs first.

- Start of inclusion: Q1 2020
- Planned last subject last follow-up visit: last subject's last visit for follow-up

For both phases and all trial arms, subjects will stay in the trial until end of trial or until confirmed disease progression, unacceptable toxicity, death or discontinuation for any other reason.

Phase IIa Arm B:

The maximum number of cycles of pembrolizumab is 18 with an approximately duration of 2 years. Then pembrolizumab will be stopped. CyPep-1 treatment may continue.

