5.3.2 Administration of Pembrolizumab

The dose of pembrolizumab in combination with CyPep-1 in the combination arm (Arm B) will be 400 mg Q6W. Pembrolizumab will be administered using IV infusion on Day 1 of each 6-week treatment cycle after all procedures and assessments have been completed.

Dosing of CyPep-1 will be aligned such that subjects will receive both pembrolizumab and the first dose of CyPep-1 on the same day (C1V1). After C1V1, pembrolizumab dosing will continue following a Q6W dosing scheme until 18 cycles, confirmed PD, unacceptable toxicity, death, or consent withdrawal. Trial treatment of pembrolizumab may be administered up to 3 days before or after the scheduled Day 1 of each cycle due to administrative reasons after the first administration (C1D1).

On the visits that CyPep-1 and pembrolizumab are administered on the same day, CyPep-1 is planned to be administered 30 to 60 min after pembrolizumab is administered. In case of pembrolizumab-related toxicity, treatment with CyPep-1 will be delayed and planned after a review by the investigator and medical monitor.

Pembrolizumab will be administered as a dose of 400 mg using a 30-minute IV infusion. Sites should make every effort to target infusion timing to be as close to 30 minutes as possible. However, given the variability of infusion pumps from site to site, a window between -5 minutes and +10 minutes is permitted (i.e., infusion time is 30 minutes [-5 min/+10 min]).

The Pharmacy Manual contains specific instructions for the preparation of the pembrolizumab infusion and administration of infusion solution.

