13.4 APPENDIX 4. VISIT ALIGNMENT

Mapping of protocol-defined visits into one common visit set for analysis purposes is presented below in [Table 10](#).

Table 10. Visit Alignment

Visit # (align.)	Visit Label (aligned)	Visit Day	Visit (per protocol)		
			Part I	Part IIa Arms A, B, C	Part IIa Arm D
1	Screening		SCREENING	SCREENING	SCREENING
2	Visit 1 Day 1	1	C1 D1	C1 D1	DAY 1
3	Visit 2 Day 8	8		C1 D8*	DAY 8
4	Visit 3 Day 15	15	C1 D15	C1 D15	DAY 15
5	Visit 4 Day 22	22		C1 D22	DAY 22
6	Visit 5 Day 29	29	C1 D29	C1 D29	
7	Visit 6 Day 36	36	C1 D36	C1 D36	
8	Visit 7 Day 43	43	C2 D1	C2 D1	
9	Visit 8 Day 50	50	C1 D50**		
10	Visit 9 Day 57	57	C2 D15	C2 D15	
11	Visit 10 Day 71	71	C2 D29	C2 D29	
12	Visit 11 Day 78	78	C2 D36	C2 D36	
13	Visit 12 Day 85	85	C3 D1	C3 D1	
14	Visit 13 Day 99	99	C3 D15	C3 D15	
15	Visit 14 Day 113	113	C3 D29	C3 D29	
16	Visit 15 Day 120	120	C3 D36	C3 D36	
17	Visit 16 Day 127	127	C4 D1	C4 D1	
18	Visit 17 Day 141	141	C4 D15	C4 D15	
19	Visit 18 Day 155	155	C4 D29	C4 D29	
20	Visit 19 Day 162	162	C4 D36	C4 D36	
21	Visit 20 Day 169	169	C5 D1	C5 D1	
22	Visit 21 Day 183	183	C5 D15	C5 D15	
23	Visit 22 Day 197	197	C5 D29	C5 D29	
24	Visit 23 Day 204	204	C5 D36	C5 D36	
25	Visit 24 Day 211	211	C6 D1	C6 D1	
26	Visit 25 Day 225	225	C6 D15	C6 D15	
27	Visit 26 Day 239	239	C6 D29	C6 D29	
28	Visit 27 Day 246	246	C6 D36	C6 D36	
29	Visit 28 Day 253	253		C7 D1	
30	Visit 29 Day 267	267		C7 D15	
31	Visit 30 Day 281	281		C7 D29	
32	Visit 31 Day 288	288		C7 D36	
33	Visit 32 Day 295	295		C8 D1	
34	Visit 33 Day 309	309		C8 D15	
35	Visit 34 Day 323	323		C8 D29	
36	Visit 35 Day 330	330		C8 D36	
37	Visit 36 Day 337	337		C9 D1	
38	Visit 37 Day 351	351		C9 D15	
39	Visit 38 Day 365	365		C9 D29	
40	Visit 39 Day 372	372		C9 D36	
41	Visit 40 Day 379	379		C10 D1	
42	Visit 41 Day 393	393		C10 D15	
43	Visit 42 Day 407	407		C10 D29	
44	Visit 43 Day 414	414		C10 D36	
45	Visit 44 Day 421	421		C11 D1	
46	Visit 45 Day 435	435		C11 D15	
47	Visit 46 Day 449	449		C11 D29	
48	Visit 47 Day 456	456		C11 D36	
49	Visit 48 Day 463	463		C12 D1	
50	Visit 49 Day 477	477		C12 D15	
51	Visit 50 Day 491	491		C12 D29	

Statistical Analysis Plan

SMS-0571/CyPep-1

V3.0 Final

04-Jun-2024

Visit # (align.)	Visit Label (aligned)	Visit Day	Visit (per protocol)		
			Part I	Part IIa Arms A, B, C	Part IIa Arm D
52	Visit 51 Day 498	498		C12 D36	
53	Visit 52 Day 505	505		C13 D1	
54	Visit 53 Day 519	519		C13 D15	
55	Visit 54 Day 533	533		C13 D29	
56	Visit 55 Day 540	540		C13 D36	
57	Visit 56 Day 547	547		C14 D1	

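### The complete-response stopping rule pairs 8 cycles with 24 weeks, but in Phase I and Arms A to C 8 cycles take 48 weeks

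*Protocol*

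**What the plan says.** Protocol 4.3.1 lists reasons for which a subject may come off study treatment while staying under observation in the study. The first is a confirmed complete response in subjects who "have been treated for at least 8 cycles (at least 24 weeks"). For combination treatment the same sentence adds a condition: 2 further cycles, with 2 pembrolizumab doses, after the complete response was first declared.

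Cycle length is fixed in several other places:

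- Protocol 5.3.2 gives pembrolizumab "on Day 1 of each 6-week treatment cycle".
- The treatment regimen part of the synopsis says for Phase I and Arms A, B and C that "CyPep-1 will be administered intratumorally Q2W, on Day 1, 15, and 29 of each cycle".
- Footnote 25 to the schedule of assessments says "CXV1 is scheduled 2 weeks after the last CyPep-1 administration".
- SAP Appendix 4 aligns the start of cycle 5 with "Visit 20 Day 169" and the start of cycle 9 with "Visit 36 Day 337".
- Protocol 3.3 says of Arm B: "The maximum number of cycles of pembrolizumab is 18 with an approximately duration of 2 years".

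**The concern.** The parenthesis reads as the duration of the 8 cycles. Eight cycles in 24 weeks means 3 weeks per cycle, and nothing in the documents sets up a 3-week cycle for this trial. As a dosing interval, 3 weeks appears only in Protocol 1.8, for the pembrolizumab regimens with which the Q6W dose is compared.

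No other passage lets a site settle the matter. The sections on treatment duration (Protocol 3.3 and 5.3.5) name progression, toxicity, death, withdrawal, loss to follow-up and trial end as reasons to stop, and set no threshold for complete responders. Two sites reading the same sentence could therefore use different minimum treatment times for such subjects.

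**Working it through.** **Inputs.** Threshold: 8 cycles, glossed as 24 weeks (Protocol 4.3.1). CyPep-1 on Days 1, 15 and 29 of each cycle (synopsis). Next cycle 2 weeks after the last CyPep-1 dose (footnote 25). Pembrolizumab every 6 weeks, once per cycle (Protocol 5.3.2). Start of cycles 2, 5 and 9 on Days 43, 169 and 337 (SAP Appendix 4).

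**Step 1: cycle length.** From the dosing days, the next cycle starts on Day 29 + 14 = Day 43, so a cycle lasts 43 − 1 = 42 days, or 6 weeks. This agrees with Protocol 5.3.2 and with Day 43 in the SAP table.

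**Step 2: try to reproduce the plan's figure.** Weeks = cycles × cycle length.

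| Cycle length | 8 cycles | 24 weeks equals |
|---|---|---|
| 2 weeks | 16 weeks | 12 cycles |
| 3 weeks | 24 weeks | 8 cycles |
| 4 weeks | 32 weeks | 6 cycles |
| 6 weeks | 48 weeks | 4 cycles |

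Of these lengths, only 3 weeks returns the stated 24 weeks.

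**Step 3: check against the SAP calendar.** Weeks elapsed = (visit day − 1) / 7.

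- Start of cycle 5 (4 cycles done): (169 − 1) / 7 = 24 weeks.
- Start of cycle 9 (8 cycles done): (337 − 1) / 7 = 48 weeks.
- Nominal ratio: 48 / 24 = 2.0.

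**Step 4: other ways to count 8 cycles.** Start of cycle 8 (Day 295): 294 / 7 = 42 weeks, ratio 1.75. Last CyPep-1 dose of cycle 8 (Day 323): 322 / 7 = 46 weeks, ratio 1.92. No count comes near 24 weeks.

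**Step 5: check the 6-week length on another stated figure.** 18 cycles × 6 = 108 weeks, and 108 × 7 / 30.4375 = 24.8 months. From first to 18th dose it is 17 × 6 = 102 weeks, or 23.5 months. Both fit about 2 years. With 3-week cycles, 18 × 3 = 54 weeks, or 12.4 months, which does not fit.

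**Step 6: scheduled doses at each threshold.** At 24 weeks: 4 × 3 = 12 CyPep-1 doses on the Q2W schedule and, in Arm B, 4 pembrolizumab doses. At 48 weeks: 24 and 8.

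**Step 7: the extra Arm B condition (illustration; the week of response is assumed).** Scans are every 8 weeks, and pembrolizumab falls at weeks 0, 6, 12, 18, 24 and so on.

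- Response first declared at week 16: the next two doses fall at weeks 18 and 24, and the second of these cycles ends at week 30. Under the 24-week reading the earliest stop is between weeks 24 and 30, against 48 under the 8-cycle reading. The ratio is 48 / 30 = 1.6 to 48 / 24 = 2.0.
- Response first declared at week 32: the next two doses fall at weeks 36 and 42, and the second cycle ends at week 48. The ratio is 48 / 48 = 1.0 to 48 / 42 = 1.14.

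**The case against.** The best defence is logical. Both limits are minimums, and a subject treated for 48 weeks has also been treated for more than 24. Read as joint conditions they do not conflict: 8 cycles governs and 24 weeks is redundant. This stands as a possible reading, but it leaves the parenthesis with no function. Its more natural reading, as the length of 8 cycles, does not fit the trial's cycles.

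It is also fair that the clause only permits stopping to be considered, and that Protocol 4.3.1 separately lets the investigator withdraw a subject from treatment at any time. That limits the consequence without removing the mismatch.

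Four stronger inferences are tempting, and the documents do not support them:

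- **That complete responders would get half of the intended treatment.** Neither 24 nor 48 weeks is an intended treatment length. Treatment runs until progression, toxicity or the other listed reasons, with pembrolizumab capped at 18 cycles. The clause sets only a floor.
- **That duration of response would be derived wrongly.** These subjects remain in follow-up. In SAP 10.1.2 and Appendix 2, stopping treatment in complete response is neither an event nor a reason for censoring; discontinuation counts only after unconfirmed progression and for progression. What is left is indirect: responses observed after different minimum exposures.
- **That a twofold difference holds in practice in every arm.** It is the nominal ratio. In Arm B the condition on dosing after response can shrink it, as Step 7 shows. For Arm D no cycle length is set, so the 8-cycle limit has no defined meaning there.
- **That the phrase about 2 cycles with 2 doses proves a 6-week cycle.** It shows one dose per cycle, which a 3-week cycle with 3-weekly dosing would also satisfy. The 6-week length rests on the sources in Steps 1 and 3.

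**Conclusion.** The mismatch is real. In Phase I and Arms A, B and C, 8 cycles take 48 weeks and 24 weeks hold 4 cycles, a nominal factor of 2 between two minimums written as one. This assumes full 6-week cycles without delays, counted to the end of the eighth. Either number could be the slip, and the documents do not show which.

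The reach is narrow: confirmed complete responders only, under a permissive rule, with no bearing on sample size, error rates or the derivation of any endpoint. The documents give no expected complete response rate, so the number of subjects affected is unknown. Arm D matters little in practice, since a footnote in SAP 6.1 records that its recruitment stopped after one subject. It is still worth correcting, because sites act on this threshold and nothing else in the protocol resolves it.

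**What to change.** In Protocol 4.3.1, reconcile the number of cycles with the number of weeks, using the 6-week cycle in Protocol 5.3.2, the synopsis dosing days with footnote 25, and SAP Appendix 4. State the cycle length on which the rule relies and whether both limits must be met. Name the arms to which it applies, including what, if anything, it means for Arm D. The choice of threshold belongs to the sponsor and is not made here. The cost is one line in a protocol amendment and notice to sites; no analysis rule in the SAP has to change.

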4.3.2 Replacement of Subjects

In Phase I, replacement for subjects who drop out for any reason, except DLTs, will only occur before the DLT observation period is completed and is allowed if a subject does not receive all three CyPep-1 administrations, unless due to CyPep-1-related toxicity.

No subject replacement will occur for subjects who withdraw later or for subjects who are part of the Phase IIa expansion monotherapy Arms A and D.

For Arm B, replacement of the first 3 subjects is allowed if a subject drops out for any reason, and does not receive all three CyPep-1 injections of the first cycle, unless due to CyPep-1 and/or pembrolizumab related toxicity (TLT) during the TLT observation period. In case of pembrolizumab-related toxicity, treatment with CyPep-1 will be delayed and planned after a review by the investigator and medical monitor. If CyPep-1 treatment is delayed > 7 days, that dose will be omitted. If the delay is > 7 days during the TLT observation period, the subject will be replaced. No subject replacement will occur for subjects who discontinue later.

For Arm C, replacement for subjects who drop out for any reason, except DLTs, before the DLT observation period is completed is allowed when a subject did not receive all three CyPep-1 administrations. No subject replacement will occur for subjects who discontinue later.

